4.2.2.2 Supportive secondary safety endpoints

- Number of treatment emergent adverse events*
- Number of treatment emergent hypoglycaemic episodes:
 - According to ADA/ISPAD classification
 - According to Novo Nordisk/ISPAD classification
- Occurrence of anti-liraglutide antibodies
- Change from baseline to 56 weeks in bone age assessment
- Change from baseline to 30 and 56 weeks and change from 56 weeks to 82 weeks in:
 - Pulse
 - Electrocardiogram (ECG)^a
 - Laboratory parameters:
 - Haematology: haemoglobin, haematocrit, thrombocytes, erythrocytes, leucocytes, differential count (eosinophils, neutrophils, basophils, lymphocytes, monocytes)
 - Biochemistry: creatinine, creatinine kinase, urea (BUN), albumin, bilirubin (total), alanine aminotransferase (ALT), aspartate aminotransferase (AST), alkaline phosphatase (ALP), sodium, potassium, calcium total, calcium, albumin- corrected, amylase, lipase, and carcinoembryonic antigen (CEA)
 - Hormone levels: calcitonin, insulin-like growth factor-1 (IGF-1), thyroid stimulating hormone (TSH), free thyroxine (free T4), dehydroepiandrosterone sulfate (DHEAS), luteinising hormone (LH), follicle stimulating hormone (FSH), estradiol (females), testosterone (males), prolactin, adrenocorticotrophic hormone (ACTH), cortisol
 - Bone metabolism markers: Type 1 collagen N-telopeptide (NTX1), type 1 C-telopeptide (CTX1), procollagen 1 N-terminal propeptide (P1NP), alkaline phosphatase (bone)
 - Pubertal status
 - Physical examination
 - Height standard deviation score (SDS)
 - Mental health assessed by Columbia Suicidality Severity Rating Scale (C-SSRS) and Patient Reported Health Questionnaire 9 (PHQ-9)

^aNot assessed at week 82 and does not have associated endpoints.

Key supportive secondary endpoint prospectively selected for disclosure (e.g., clinicaltrials.gov and EudraCT) are marked with an asterisk (*)

5 Trial design

5.1 Type of trial

This is a 56-week double-blind, randomised, parallel-group, placebo-controlled, multi-national trial followed by a 26-week period off study-drug. The trial will be conducted in pubertal adolescents with obesity aged 12 to less than 18 years. Subjects will be randomised 1:1 to receive liraglutide or placebo. The randomisation will be stratified according to pubertal and glycaemic status (see Sections 5.2 and 11).

At least 30% of subjects will be from areas with lifestyle and nutrition comparable to those in the European Union. All subjects will undergo counselling in healthy nutrition and physical activity for weight loss and must be prescribed a structured programme from the beginning of the 12-week run-in period and continuing through the 26-week follow-up period off trial drug. The trial design is shown schematically below:

[figure not shown]

Figure 5-1 Trial design

5.2 Rationale for trial design

This trial is designed in accordance with regulatory requirements³⁵ and guidelines^{34, 36}

The primary endpoint, change in BMI SDS, is selected based on EMA's recommendation for a primary endpoint in the assessment of efficacy of new medicinal products for the treatment of obesity in children³⁴. The primary endpoint is assessed at the end of the 56 week double blind period. Secondary endpoints are assessed at the end of 30, 56, and 82 weeks. The assessment of secondary endpoints at 30 weeks, including BMI SDS, is included as there is a likelihood of a high attrition rate in this population of adolescents. Efforts will be made to encourage retention.

First-line therapy in primary obesity should always be lifestyle modification, rather than pharmacotherapy. To reflect this, a 12-week run-in period has been included in the trial design. During the run-in period, a structured counselling programme in healthy nutrition and physical activity is implemented in alignment with CHMP guidelines³⁴.

The 56-week treatment period is designed to be double-blind in order to avoid/minimise bias during the assessment of the primary endpoint. Randomisation is another measure used to minimise bias and is expected to lead to comparable subject populations at baseline in the liraglutide and placebo groups. Stratification according to Tanner staging as described in Section 8.4.7 will be used to enable the examination of treatment effect consistency across trial population subgroups. Stratification will also be performed according to glycaemic status: normoglycaemia versus dysglycaemia (pre-diabetes and T2DM).

Table 5–1 Glycaemic category

Normoglycaemia	FPG <5.6 mmol/L (<100 mg/dL) and/or HbA _{1c} <5.7%
Pre-diabetes	FPG 5.6–6.9 mmol/L (both inclusive), FPG 100–125 mg/dL (both inclusive) or HbA _{1c} 5.7–6.4% (both inclusive)
Type 2 diabetes (T2DM)	FPG ≥7.0 mmol/L (≥126 mg/dL) and/or HbA _{1c} ≥6.5%

Adapted from³⁷

The stratification is controlled by interactive web response system (IWRS); see Section 11.

Dysglycaemia is expected to occur frequently in this trial population. No interaction was observed between glycaemic status and body weight in the adult trial (NN8022-1839: Effect of liraglutide on body weight in non-diabetic subjects with obesity or overweight subjects with co-morbidities), and a similar pattern of AEs was observed in sub-populations by pre-diabetes status at screening.

The 56-week duration of liraglutide treatment is consistent with regulatory authorities' recommendations for the estimation of safety and stabilisation of treatment effect of a weight-management product (1 year) and also includes a 4-8 week dose escalation period^{34, 38}.

The 26-week duration of the off-study-drug follow-up period is aligned with regulatory recommendations³⁴ and is considered to be sufficient to assess effect maintenance and any evidence of rebound, as well as to monitor post-treatment safety.

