8.3.1 Body measurements

8.3.1.1 Body weight

Body weight must be measured to the nearest 0.1 kg or 0.1 pounds. Fasting body weight must be measured at the fasting visits (Section [8.1.2](#)). If the weight is not measured fasting at fasting visits, the subject must be called in for a new visit within the visit window to have the fasting weight measured. At the remaining visits, the measurement is performed in a non-fasting state.

The same digital scale should be used throughout the trial. The scale must be calibrated according to the directions for use and, as a minimum, once a year.

Weight should be measured without shoes and only wearing light clothing and the subject should have an empty bladder.

Weight measured at screening is used for the calculation of BMI, whereas weight measured at randomisation is used as baseline for assessment of change in body weight. BMI is calculated in the eCRF.

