The subject and any biological material obtained from the subject will be identified by subject number and trial ID. Appropriate measures such as encryption or leaving out certain identifiers will be enforced to protect the identity of subjects in all presentations and publications as required by local, regional and national requirements.

16 Computerised systems

Novo Nordisk will capture and process clinical data using computerised systems that are described in Novo Nordisk Standard Operating Procedures and IT architecture documentation. The use and control of these systems are documented.

Investigators working on the trial may use their own electronic systems to capture source data.

17 Statistical considerations

If necessary, a statistical analysis plan (SAP) may be written in addition to the protocol, including a more technical and detailed elaboration of the statistical analyses. The SAP will be finalised before database lock.

Results from the statistical analysis will generally be presented by two-sided confidence intervals (CIs) with a confidence level of 95%. Superiority will be claimed if the two-sided p-value is less than 5% and the treatment estimate favours liraglutide.

The full analysis set (FAS) will be used in the analysis of the efficacy endpoints. For the safety endpoints, the safety analysis set (SAS) will be used. The definition of the analysis sets are given in Section [17.2](#).

Laboratory values below the lower limit of quantification (LLOQ) will be set to $\frac{1}{2}$ LLOQ.

The baseline value will be defined as the last measured and available value from randomisation (V9) and end of run-in (V8), if not otherwise specified.

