17.1 Sample size calculation

This is a superiority trial comparing liraglutide to placebo. Superiority will be claimed if the p-value is less than 5% and the treatment favours liraglutide.

It is anticipated that the effect of liraglutide in adolescents with obesity will be similar to the effect observed in adults. The anticipated treatment difference for BMI SDS³³ is based on the results from trial NN8022 1839 in adults with overweight and obesity. For the sample size scenarios, treatment differences of -0.24, -0.26, and -0.28 were investigated.

The standard deviation (SD) is assessed based on publications by Reinehr et al. 2009¹³ Berkowitz et al. 2003⁵⁶ and trial NN8022-3967 in adolescents with obesity aged 12–17 years. For the sample size scenarios, SD of 0.25, 0.35 and 0.45 were investigated.

The effect of withdrawals on the analysis is accounted for as a reduction of the anticipated treatment difference and increase of the SD. Since a conservative imputation method is planned for the main analysis of the primary endpoint, it is assumed that withdrawn subjects respond as if treated with placebo for the entire trial. The assumed withdrawal percentage for this paediatric trial is 40% at week 56. A higher withdrawal percentage is assumed for this trial than what was seen in trial NN8022-1839 in adults, because this trial will include an adolescent trial population.

The total number of subjects is shown for the investigated scenarios in [Table 17–1](#) for 90% and 99% power.

Table 17–1 Sample size calculations for different scenarios with total number of randomised subjects

POWER	Treatment difference (completers)	SD		
		0.25	0.35	0.45
90%	-0.24	144	266	428
	-0.26	124	228	366
	-0.28	110	200	318
99%	-0.24	248	462	746
	-0.26	216	398	638
	-0.28	190	346	554

Based on the above mentioned references, it seems realistic and conservative to assume an SD of 0.35 and a treatment difference of –0.26. The minimum requirement in the Paediatric Investigation Plan is 154 randomised subjects while FDA requires a minimum of 100 subjects exposed to liraglutide. A sample size of 228 randomised subjects gives a power of 90%. Thus, the number of randomised subjects should be 228.

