17.3 Primary endpoint

The primary endpoint is change from baseline in BMI SDS after 56 weeks of treatment³³.

The objective is to show that liraglutide is superior to placebo in obtaining weight loss. Let $\mu_{\text{liraglutide}}$ and μ_{placebo} denote the mean change in BMI SDS for liraglutide and placebo, respectively. The null-hypothesis and the alternative hypothesis are:

H0: $\mu_{\text{liraglutide}} = \mu_{\text{placebo}}$ against the alternative HA: $\mu_{\text{liraglutide}} \neq \mu_{\text{placebo}}$

The null-hypothesis will be rejected on a 5% level if the two-sided 95% CI of the treatment difference $\mu_{\text{liraglutide}} - \mu_{\text{placebo}}$ excludes 0. If the upper limit is below 0, superiority of liraglutide against placebo can be concluded.

The hypothesis will be tested using an analysis of covariance (ANCOVA) model with treatment, sex, region, baseline glycaemic category, stratification factor for Tanner stage and interaction between baseline glycaemic category and stratification factor for Tanner stage as fixed effects, and baseline BMI SDS and baseline age as covariates. The baseline glycaemic category includes two levels: presence and absence of dysglycaemia. The stratification factor for Tanner stage includes two levels: stages 2 and 3 together, and stages 4 and 5 together.

Missing data in the main analysis will be handled by the following multiple imputation (MI) method. A pattern mixture model approach is applied where withdrawn subjects without a follow-up visit are assumed to respond as if treated with placebo for the entire trial. Multiple copies (100 copies) of the full dataset will be generated by imputing missing values based on estimated parameters for the placebo group. This will be done as follows:

- In the first step, 100 copies of the dataset will be generated.
- In the second step, an enriched ANCOVA model with sex, region, baseline glycaemic category, stratification factor for Tanner stage and interaction between baseline glycaemic category and stratification factor for Tanner stage as fixed effects and baseline BMI SDS, baseline waist circumference, baseline age and baseline HbA_{1c} as covariates will be fitted to the change from baseline in BMI SDS at 56 weeks for the completers in the placebo group only.

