The imputation model in step 2 uses placebo subjects from FAS with non-missing BMI SDS at baseline and week 56. The imputation model is a linear regression of BMI SDS at week 56 on the factors and covariates listed in [Table 2-3](#) (except randomised treatment arm) with interaction term included in the model. The order of the factors and covariates has been retained as mentioned in [Table 2-3](#) while fitting imputation model. The estimated posterior distribution for the parameters (regression coefficients and variances) in the imputation model is then used to impute missing week 56 BMI SDS values for both randomised treatment arms.

Table 2-3: Factors and Covariate for imputation model

Factors and covariates at baseline	Type	Categories	Order
Sex	Factors	Female, Male	1
Region	Factors	Europe, North America	2
Baseline Glycaemic category	Factors	Yes, No	3
Tanner stage	Factors	Stage 2 and 3 together, Stage 4 and 5 together	4
Tanner stage, Glycaemic category	Interaction factor	Not applicable	5
Baseline BMI SDS	Covariate	Not applicable	6
Baseline Waist circumference	Covariate	Not applicable	7
Baseline Age	Covariate	Not applicable	8
Baseline HbA1c	Covariate	Not applicable	9

The multiple imputations will be generated using Novo Nordisk trial number 80224180 as seed number.

A similar procedure of imputation will be followed for all the secondary endpoints as mentioned in [Table 2-4](#) except while imputing missing values for waist circumference assessment, baseline waist circumference which will not be included in the imputation model. Similarly, for HbA_{1c} assessments, baseline HbA_{1c} will not be included in the imputation model.

For missing glycaemic category, the imputation will be done for missing FPG and HbA_{1c} assessments using the imputation model mentioned in [Table 2-4](#) except for HbA_{1c}, baseline HbA_{1c} which will not be used while imputing the missing values.

Table 2-4: Statistical analysis to address primary and secondary objectives

SI No.	Endpoints	Landmark visits	Endpoint type	Imputation approach and Statistical model	Analysis set	Sensitivity analyses
Primary Endpoint						
1	Change from baseline in BMI SDS	Week 56	Continuous	J2R-MI ANCOVA	FAS	
 • ANCOVA (LOCF) • ANCOVA (BOCF) • ANCOVA (no imputation, with 56 week completers) • MMRM
Secondary Endpoint						
2	Change from baseline in BMI SDS	Week 30, Week 82	Continuous	J2R-MI ANCOVA	FAS	NA

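### Free improvement: screening BMI SDS is collected but left out of the primary ANCOVA, the imputation model and the MMRM; the gain from adding it is unknown and may be small

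*Protocol*

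**What the plan says.** - **Run-in.** Protocol 5.2 explains that lifestyle change comes before drug treatment: "To reflect this, a 12-week run-in period has been included in the trial design". Under protocol 5.3 the same counselling then runs through the blinded period and the follow-up.
- **Data before randomisation.** Inclusion criterion 3 needs a BMI at screening, and randomisation criterion 1 needs one at the end of run-in. Protocol 8.3.1.1 states: "Weight measured at screening is used for the calculation of BMI". SAP Table 3-2 lists height at V2, V8 and V9.
- **Baseline.** Protocol section 17 and SAP section 2 take the last available value from V9 and V8. SAP 2.3.1 lets a screening value stand in when the randomisation value is missing.
- **Primary model.** Protocol 17.3 adjusts for sex, region, glycaemic category, Tanner stratum and the interaction of the last two, "and baseline BMI SDS and baseline age as covariates". SAP Table 2-1 lists the same terms.
- **Imputation model.** SAP 2.3.2: "The imputation model is a linear regression of BMI SDS at week 56 on the factors and covariates listed in" Table 2-3. That table adds only baseline waist circumference and baseline HbA1c to the covariates of the primary model.
- **Sensitivity analyses.** The LOCF, BOCF and completer ANCOVAs use the covariates of the primary model. So does the MMRM, whose responses are all post-baseline. None contains a screening or run-in term.

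**The concern.** The change from V2 to V9 is a pre-randomisation reading of how a subject responds, mostly under the counselling that both arms go on receiving. It is a plausible predictor of the week-56 change. It is also relevant to imputation, because the placebo-based model predicts week-56 values from baseline characteristics alone and the sizing assumes 40% withdrawal. The protocol already accepts the principle by enriching that model with waist and HbA1c, yet it leaves out an earlier value of the endpoint itself. What may be lost is precision: a wider confidence interval for the primary difference, and imputed values less specific to the subject. Type I error and the estimand are not affected.

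**Working it through.** **Inputs from the documents.** Two-sided 5% test (protocol section 17: "Superiority will be claimed if the two-sided p-value is less than 5% and the treatment estimate favours liraglutide"). In protocol 17.1, "treatment differences of -0.24, -0.26, and -0.28 were investigated" for completers, and for the chosen scenario "it seems realistic and conservative to assume an SD of 0.35 and a treatment difference of" −0.26. Withdrawal is 40%, with withdrawn subjects responding as placebo. Allocation is 1:1. Stated result: "A sample size of 228 randomised subjects gives a power of 90" per cent.

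**Assumed inputs.** r, the partial correlation of the V2-to-V9 change with the week-56 change given the existing covariates, is not in the documents; the range used is 0 to 0.4. The SD of 0.35 is read as the residual SD under the planned covariates, because protocol 17.1 does not say whether it is adjusted.

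**Step 1: reproduce the plan.**
- Diluted difference: 0.6 × 0.26 = 0.156.
- Placebo variance: 0.35² = 0.1225.
- Liraglutide variance: 0.1225 + 0.4 × 0.6 × 0.26² = 0.1225 + 0.0162 = 0.1387. The second term arises because 60% of that arm has the effect and 40% does not.
- Standard error at 114 per arm: √[(0.1387 + 0.1225)/114] = 0.0479.
- A two-sample t-test (noncentral t, 226 df) gives 90.1% power, and 228 is the smallest total that reaches 90%. The same method reproduces all 18 cells of Table 17-1.

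**Step 2: add the covariate.** Screening BMI SDS next to V9 BMI SDS is linearly equivalent to adding the V2-to-V9 change. The residual variance becomes 0.1225 × (1 − r²). The mixture term 0.0162 is left unchanged, because it comes from withdrawal status and not from residual variation in response. For r = 0.3: 0.1225 × 0.91 = 0.1115; standard error √[(0.1115 + 0.0162 + 0.1115)/114] = 0.0458.

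| r (assumed) | Power at 228 | Total N for 90% | 95% CI half-width (BMI SDS) |
|---|---|---|---|
| 0 | 90.1% | 228 | 0.0938 |
| 0.1 | 90.3% | 226 | 0.0934 |
| 0.2 | 91.1% | 220 | 0.0920 |
| 0.3 | 92.4% | 210 | 0.0898 |
| 0.4 | 94.1% | 194 | 0.0865 |

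Half-width is 1.96 times the standard error. Shrinking the mixture term as well would give 91.2%, 92.5% and 94.3% at r = 0.2, 0.3 and 0.4, which is at most 0.2 points higher.

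**Step 3: check under the planned type of imputation.** A simulation of placebo-based multiple imputation used 1,500 trials per case, 25 imputations (the plan uses 100), 40% missing at random and Rubin pooling. Adding the covariate moved the mean pooled standard error from 0.0567 to 0.0560 at r = 0.2, from 0.0568 to 0.0547 at r = 0.3, and from 0.0570 to 0.0528 at r = 0.4. Those are falls of about 1%, 4% and 7%. At r = 0 there was no gain (0.0569 and 0.0571). These standard errors exceed the 0.0479 of Step 1 because they include imputation variance, which the sizing calculation leaves out. The simulation is used only for direction and relative size.

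**The case against.** The strongest reply is that nothing is broken. The planned power reproduces without this covariate, the sizing text takes no explicit credit for covariate adjustment, and the models already hold end-of-run-in BMI SDS with a reasonable set of prognostic factors. One more covariate is then a preference, with a benefit that rests on a number nobody has supplied. This stands as to certainty and size. Some design features may also keep r low: self-reported weight must be stable before screening, obesity must still be present after run-in, and run-in compliance is judged before randomisation. Subjects who stop trial product are asked back at week 56 and those values are used, so the share actually imputed may be below 40%.

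A reader might also infer stronger things that the documents do not support:

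- **That power is known to be lost, or that the 90% is overstated.** The first needs a value of r that is not given. The second is contradicted by Step 1.
- **That the V2 value corrects measurement error in the V9 baseline.** V2 is about 14 weeks earlier with an intervention in between, so it is not a replicate. Random baseline error does not bias a randomised ANCOVA contrast, and the documents give no sign that it is material.
- **That the omission biases the estimate through withdrawal.** That would need withdrawal to depend on run-in response differently in the two arms. The documents say nothing on this.
- **That the variable is exactly the 12-week run-in change.** Run-in starts at V3 (week −12), while SAP Table 3-2 lists height at V2 (week −14) and not at V3. The derivable change runs from screening to randomisation.

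None of this removes the case for a prognostic covariate that is already collected and costs almost nothing to add.

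**Conclusion.** The point holds as a free improvement, not as an error in the plan. The primary ANCOVA, the imputation model and the MMRM omit a pre-randomisation value of the endpoint that should exist for every randomised subject. Adding it leaves the estimand and the validity of the test unchanged. Against the planned 90.1%, the gain is 0.2 points at r = 0.1, 1.0 at r = 0.2, 2.3 at r = 0.3 and 4.0 at r = 0.4; at r = 0 one degree of freedom is lost. The result rests on the assumed r, on reading 0.35 as the residual SD, and on V2 weight and height being recorded as protocol 8.3.1.1 and SAP Table 3-2 indicate. The flowchart rows for weight and height were not available to check this.

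**What to change.** Before unblinding:

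1. Add screening (V2) BMI SDS as a covariate in protocol 17.3, SAP Table 2-1, SAP Table 2-3 and the MMRM. Keep V9 (otherwise V8) as the baseline from which change is measured.
2. Use the V2 value in the same way for the BMI and body weight endpoints.
3. State a rule for subjects whose baseline is replaced by the screening value under SAP 2.3.1. For them the two covariates coincide and the run-in change is zero by construction. The rule should also say whether V8 takes precedence over screening, since SAP section 2 names V8 and SAP 2.3.1 names screening.

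The cost is SAP wording, one extra parameter in the ANCOVA and in the imputation model, and one per visit in the MMRM, where covariates are nested under visit. No new data are needed, and the sample size need not change.

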9.5 Auxiliary supplies

The following will be provided by Novo Nordisk in accordance with the TMM:

- Direction for use for PDS290 pen-injector for trial product
- Needles for the device (maximum length to be used is 8 mm)
- BG meters and BG-meter auxiliary supplies

Only needles provided by Novo Nordisk must be used for administration of trial product.

10 Interactive web response system

A trial-specific IWRS will be set up which can be accessed at any time via the internet or telephone. Access to the IWRS must be restricted to and controlled by authorised persons.

IWRS is used for:

- Screening
- Screening failure
- Randomisation
- Medication arrival
- Dispensing
- Treatment discontinuation
- Completion
- Code break
- Drug accountability
- Data change

IWRS user manuals will be provided to each trial site.

11 Randomisation procedure and breaking of blinded codes

At randomisation, the subjects will be randomised to one of two parallel treatment groups: liraglutide 3.0 mg or placebo. The randomisation will be carried out in a 1:1 manner using the IWRS.

The randomisation will be stratified according to pubertal and glycaemic status (see Sections [5.2](#)). Stratification will be controlled by the IWRS. The strata are:

Table 11–1 Strata

Tanner 2 or 3	Dysglycaemia yes
Tanner 2 or 3	Dysglycaemia no
Tanner 4 or 5	Dysglycaemia yes
Tanner 4 or 5	Dysglycaemia no

Dysglycaemia is defined as T2DM or pre-diabetes with FPG ≥ 5.6 mmol/L (≥ 100 mg/dL) and/or HbA_{1c} $\geq 5.7\%$ (see [Table 5–1](#)). The laboratory results from V8 must be used for this purpose.

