The change in glycaemic category (normoglycaemia, pre-diabetes, T2DM) from baseline at 30 and 56 weeks and change from 56 weeks to 82 weeks will be summarised using descriptive statistics.

Furthermore, two separate analyses will be performed on the binary variable normoglycaemia (yes/no) at 30 and 56 weeks, using a logistic regression model with the factors treatment, sex, region, baseline glycaemic category, stratification factor for Tanner stage and interaction between baseline glycaemic category and stratification factor for Tanner stage, and baseline age as covariate. Missing data will be handled by an MI method similar to the one used for the main analysis of the primary endpoint, but adapted to the logistic regression model. The results will be presented as odds ratios together with the associated 95% CIs.

Other supportive secondary efficacy endpoints

The following other efficacy variables will be evaluated:

- Body weight
- Waist circumference
- Waist-to-hip circumference ratio
- Cardiovascular biomarker (hsCRP)

- Fasting lipids (TC, LDL-cholesterol, HDL-cholesterol, non-HDL cholesterol, VLDL cholesterol, TG and FFA)
- Systolic and diastolic blood pressure
- Quantitative glucose metabolism parameters (HbA_{1c}, FPG, fasting insulin, fasting C-peptide, HOMA-B^a and HOMA-IR^a)

The changes in these variables from baseline at 30 and 56 weeks will be analysed using the same type of ANCOVA with MI as used for the main analysis of the primary endpoint, but with the baseline value of the corresponding variable instead of the baseline BMI SDS as covariate. Each endpoint will be analysed separately. For hsCRP, fasting lipids, fasting insulin, fasting C-peptide, HOMA-B and HOMA-IR, the response and baseline values will be log transformed prior to the analysis. The change in these variables from 56 weeks to 82 weeks will be summarised using descriptive statistics.

^a The calculation of the HOMA endpoints will be done as follows:

- Beta-cell function (%) = $20 \cdot \text{fasting insulin}[\text{mU/L}] / (\text{FPG}[\text{mmol/L}] - 3.5)$
- Insulin resistance (%) = $\text{fasting insulin} [\text{mU/L}] \cdot \text{FPG} [\text{mmol/L}] / 22.5$.

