3	Change from baseline in BMI SDS (%)	Week 30, Week 56	Continuous	J2R-MI ANCOVA	FAS	NA
4	Change from baseline in BMI SDS	Week 56 to 82 (Week 56 as baseline)	Continuous	J2R-MI ANCOVA	FAS	NA
5	Change from baseline BMI	Week 30, Week 56	Continuous	J2R-MI ANCOVA	FAS	NA

	(Kg/m ²)					
6	Percentage of Subjects achieving $\geq 5\%$ reduction in baseline BMI	Week 30, Week 56, Week 82	Categorical	J2R-MI Logistic Regression	FAS	NA
7	Percentage of Subjects achieving $\geq 10\%$ reduction in baseline BMI	Week 30, Week 56, Week 82	Categorical	J2R-MI Logistic Regression	FAS	NA
8	Change from Baseline in PRO score (IWQoL)	Week 30, Week 56	Continuous	J2R-MI ANCOVA	FAS	NA
9	Change from baseline in Glycaemic category	Week 30, Week 56	Categorical	J2R-MI Logistic Regression	FAS	NA
10	Change from baseline in Body weight (kg and %)	Week 30, Week 56	Continuous	J2R-MI ANCOVA	FAS	NA
11	Change from baseline in Waist circumference (cm)	Week 30, Week 56	Continuous	J2R-MI ANCOVA	FAS	NA
12	Change from baseline in Waist-to-hip circumference ratio (ratio)	Week 30, Week 56	Continuous	J2R-MI ANCOVA	FAS	NA
13	Change from baseline Systolic Blood Pressure (mmHg)	Week 30, Week 56	Continuous	J2R-MI ANCOVA	FAS	NA
14	Change from	Week 30,	Continuous	J2R-MI	FAS	NA

	baseline Diastolic Blood Pressure (mmHg)	Week 56		ANCOVA		
15	Change from baseline Pulse (beats/min)	Week 30, Week 56	Continuous	J2R-MI ANCOVA	SAS	NA
16	Change from baseline in Cardiovascular biomarker (hsCRP) (mg/L)	Week 30, Week 56	Continuous	J2R-MI ANCOVA (with log transformed response and baseline values)	FAS	NA
17	Change from baseline in TC (mmol/L)	Week 30, Week 56	Continuous	J2R-MI ANCOVA (with log transformed response and baseline values)	FAS	NA
18	Change from baseline in LDL-cholesterol (mmol/L)	Week 30, Week 56	Continuous	J2R-MI ANCOVA (with log transformed response and baseline values)	FAS	NA
19	Change from baseline in HDL-cholesterol (mmol/L)	Week 30, Week 56	Continuous	J2R-MI ANCOVA (with log transformed response and baseline values)	FAS	NA
20	Change from baseline in non-HDL cholesterol (mmol/L)	Week 30, Week 56	Continuous	J2R-MI ANCOVA (with log transformed response and baseline values)	FAS	NA
21	Change from baseline in VLDL (mmol/L)	Week 30, Week 56	Continuous	J2R-MI ANCOVA (with log transformed response and baseline values)	FAS	NA
23	Change from baseline in TG (mmol/L)	Week 30, Week 56	Continuous	J2R-MI ANCOVA (with log transformed response and baseline values)	FAS	NA

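### Table 5-1 calls a subject normoglycaemic on one normal marker, which contradicts Section 11 and would misclassify the supportive week 30 and 56 normoglycaemia outcome if coded as written

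*Protocol*

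**What the plan says.** **Definition.** Protocol Section 5.2, Table 5-1, has three rows. The normoglycaemia row reads "FPG <5.6 mmol/L (<100 mg/dL) and/or HbA" and goes on to HbA1c below 5.7%. The pre-diabetes row is met by FPG 5.6–6.9 mmol/L or HbA1c 5.7–6.4%. The T2DM row is met by FPG of at least 7.0 mmol/L and/or HbA1c of at least 6.5%.

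**Stratification.** Section 5.2 gives the glycaemic split as "normoglycaemia versus dysglycaemia (pre-diabetes and T2DM"). Section 11 says "Dysglycaemia is defined as T2DM or pre-diabetes with FPG" at or above 5.6 mmol/L and/or HbA1c at or above 5.7%, refers to Table 5-1, and uses the V8 laboratory results.

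**Baseline factor.** Section 17.3: "The baseline glycaemic category includes two levels: presence and absence of dysglycaemia". SAP Table 2-1 codes the same factor as dysglycaemic or non-dysglycaemic. SAP 3.1 takes it from the randomisation visit.

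**Outcome.** Section 17.4.1.1 summarises the three-level category and adds that "two separate analyses will be performed on the binary variable normoglycaemia (yes/no) at 30 and 56 weeks", by logistic regression with baseline glycaemic category among the factors. It gives no cut-offs and no cross-reference. SAP Table 2-4 lists the endpoint as "Change from baseline in Glycaemic category", and SAP 2.4 points back to protocol Section 17.4.

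**Missing values.** SAP 2.3.2: "For missing glycaemic category, the imputation will be done for missing FPG and HbA"1c. No sentence says how the two values become a category. SAP 2.5, which holds the endpoint derivations, does not cover glycaemic category.

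**The concern.** Two rules meant to describe opposite states cannot both be satisfied by one abnormal marker. Under Table 5-1 a single normal marker makes a subject normoglycaemic. Under Section 11 a single abnormal marker makes the same subject dysglycaemic.

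For the baseline factor, Section 11 settles the matter with an explicit rule. For weeks 30 and 56 nothing does. The outcome carries the name normoglycaemia, and the only place that defines this word is the faulty row. A programmer who follows it would produce an outcome that disagrees with the baseline factor in the same model. A subject whose FPG and HbA1c never change could enter as dysglycaemic and be counted as normoglycaemic at week 56. Glycaemic control is a stated secondary objective, and odds ratios with 95% confidence intervals are planned for this outcome.

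**Working it through.** The plan states no figure to reproduce here. The check is an enumeration of the definitions.

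**Step 1: inputs.** FPG bands from Table 5-1: below 5.6, 5.6–6.9, and 7.0 mmol/L or more. HbA1c bands: below 5.7, 5.7–6.4, and 6.5% or more. This gives 3 × 3 = 9 cells.

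**Step 2: apply both rules.** N, P and T mark the Table 5-1 rows that each cell meets (normoglycaemia, pre-diabetes, T2DM).

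| FPG band | HbA1c band | Table 5-1 rows met | Section 11 laboratory rule | Conflict |
|---|---|---|---|---|
| <5.6 | <5.7 | N | not dysglycaemic | no |
| <5.6 | 5.7–6.4 | N, P | dysglycaemic | yes |
| <5.6 | ≥6.5 | N, T | dysglycaemic | yes |
| 5.6–6.9 | <5.7 | N, P | dysglycaemic | yes |
| 5.6–6.9 | 5.7–6.4 | P | dysglycaemic | no |
| 5.6–6.9 | ≥6.5 | P, T | dysglycaemic | no |
| ≥7.0 | <5.7 | N, T | dysglycaemic | yes |
| ≥7.0 | 5.7–6.4 | P, T | dysglycaemic | no |
| ≥7.0 | ≥6.5 | T | dysglycaemic | no |

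The literal normoglycaemia row covers 5 cells. The complement of the Section 11 laboratory rule covers 1. The difference, 5 − 1 = 4 cells, is both normoglycaemic and dysglycaemic, and 2 of those 4 also meet the T2DM row. Two further cells meet the pre-diabetes and T2DM rows together; they matter only for the three-level descriptive summary.

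Example: FPG 5.2 mmol/L with HbA1c 5.9% is normoglycaemic and pre-diabetic within Table 5-1, and dysglycaemic under Section 11.

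**Step 3: require both markers to be normal.** The normoglycaemia row then covers only the first cell, and the conflict falls from 4 cells to 0.

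**Step 4: how many subjects.** The cells are unweighted, and the documents do not say how many subjects have exactly one abnormal marker. As an illustration only, take latent bivariate normal markers with abnormal proportions *p* (FPG) and *q* (HbA1c):

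P(exactly one abnormal) = *p* + *q* − 2 × P(both abnormal)

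Assumed ranges: *p* 2–30%, *q* 5–40%, correlation 0.3–0.6.

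- Lowest (*p* = 0.02, *q* = 0.05, correlation 0.6): 0.02 + 0.05 − 2 × 0.0081 = 0.054, or about 12 of 228.
- Highest (*p* = 0.02, *q* = 0.40, correlation 0.3): 0.02 + 0.40 − 2 × 0.0138 = 0.392, or about 89 of 228.

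Other assumptions move the range. With 70–90% of subjects normal on each marker and correlation 0–0.6, the normoglycaemic proportion is 49–84% if both markers must be normal and 83–99% if one is enough. At equal inputs the gap is 12–42 percentage points. The width of these ranges shows that the size cannot be fixed from the documents.

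**The case against.** The strongest reply is that the intended meaning can be recovered. Section 5.2 opposes the two states, Section 17.3 and SAP Table 2-1 use presence or absence of dysglycaemia, and the literal row would label some subjects both normoglycaemic and T2DM. A careful programmer would notice and probably code the complement. This stands in part: the harm arises only if the row is followed as written. But no sentence applies the Section 11 rule to weeks 30 and 56, and the outcome is named after the ambiguous row. One might also say that the conjunction was meant for subjects with only one marker measured. No passage says so, and the SAP imputes both markers, so the imputed datasets hold both values and need a combining rule.

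Three stronger readings are tempting, and the documents do not support them.

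- *That the outcome has no definition at all.* Table 5-1 is titled as the glycaemic category, and its three labels recur in Section 17.4.1.1. A definition exists; one row of it is faulty, and it is neither cross-referenced nor completed by a combining rule.
- *That stratification or the primary analysis is compromised.* Section 11 has its own explicit laboratory rule, and the primary ANCOVA uses the two-level dysglycaemia factor.
- *That the withdrawal assumption measures the problem.* Section 17.1 says "The assumed withdrawal percentage for this paediatric trial is 40% at week 56", and 0.40 × 228 = 91.2. That counts withdrawals, whereas the classification conflict applies equally to observed and imputed values.

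**Conclusion.** The point holds and is minor. As written, Table 5-1 contradicts Sections 5.2 and 11 in 4 of 9 marker combinations. Coding it literally would count as normoglycaemic, at weeks 30 and 56, subjects whose marker values the baseline factor treats as dysglycaemic. Neither SAP 2.3.2 nor SAP 2.5 repairs this.

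The cell count rests on the documents alone. Any number of affected subjects rests on assumed prevalences and correlation. The consequence is confined to a supportive endpoint that is not among the asterisked key endpoints, and to the descriptive category summaries. HbA1c and FPG are also analysed as continuous variables, which the conflict does not touch.

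One limit on wording: Section 11 can be parsed so that diagnosed T2DM counts as dysglycaemia whatever the laboratory values, and Section 5.3 admits subjects with diagnosed T2DM. Normal values on both markers are therefore the complement of the Section 11 *laboratory* rule, and not necessarily of the baseline factor in every subject. For this reason the repair should not re-derive the baseline factor.

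**What to change.** 1. In the normoglycaemia row of Table 5-1, replace the conjunction with a plain 'and', so that the row agrees with the laboratory rule in Section 11.
2. Add to SAP 2.5: for the week 30 and 56 outcome, and for the week 82 descriptive category, a subject is normoglycaemic only if FPG is below 5.6 mmol/L and HbA1c is below 5.7%. This applies to observed values and to values imputed under SAP 2.3.2.
3. Add that, in the three-level summary, the worse category is used when the markers disagree.

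Leave unchanged the baseline stratification factor, the thresholds, the T2DM row, and the handling of subjects who develop T2DM in Section 5.3.

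Cost: two sentences in the SAP and one conjunction in a table row, settled before database lock. No new data and no change to the primary analysis.
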